team will be			discussions to	around	
proactive in			monitor equity	qualitative	
regularly inviting			and access.	work, ensuring	
feedback and				that evaluation	
discussion around			Evaluation	team engage in	
the accessibility of			team will also	reflexive	
the project and			ensure ongoing	process around	
any other equity			learning	acknowledging	
concerns that may			around equity	bias around	
be raised by			and	data collection	
participants or the			incorporate	and analysis.	
delivery team.			learning from		
Wider researcher discussion will also			other projects.		

take place with the team, such as exploring and mitigating for bias when analysing research data and when discussing equity in meetings.				
Next steps Both delivery and evaluation teams will highlight any relevant next steps in relation to further research or practical implications for the implementation of MDFT that are linked to equity.	Throughout study and recommendations formulated for any further work.	All	Definitive tasks around next steps pertaining to equity in future research and implementation will ensure that any potential gaps in representation of under-served groups are minimised both in relation to the current project and other future work.	Ongoing

Please share your completed form with the evaluation manager for your project.

Appendix IV: Outcomes not contained with YEF Core Outcome Dataset

GAIN-SS – Substance Use

The following questions are about common psychological, behavioral, and personal problems. These problems are considered significant when you have them for two or more weeks, when they keep coming back, when they keep you from meeting your responsibilities, or when they make you feel like you can't go on. After each of the following questions, please tell us the last time, if ever, you had the problem by answering whether it was in the past month, 2 to 3 months ago, 4 to 12	Past month	2 to 3 months ago	4 to 12 months ago	1+ years ago	Never
months ago, 1 or more years ago, or never.	4	3	2	1	0
When was the last time that a. you used alcohol or other drugs weekly or more often? b. you spent a lot of time either getting alcohol or other drugs, using alcohol or other drugs, or recovering from the effects of alcohol or other drugs (e.g., feeling sick)?			2	1	0
c. you kept using alcohol or other drugs even though it was causing social problems, leading to fights, or getting you into trouble with other people?	4	3	2	1	0
d. your use of alcohol or other drugs caused you to give up or reduce your involvement in activities at work, school, home, or social events?	4	3	2	1	0
e. you had withdrawal problems from alcohol or other drugs like shaky hands, throwing up, having trouble sitting still or sleeping, or you used any alcohol or other drugs to stop being sick or avoid withdrawal problems?	4	3	2	1	0

DUE - Drug Use Expectancy

Positive and negative expectancies

Strongly disagree

For each of the following questions, circle the answer closest to how you think?

Disagree

Q1. Using substances can have a lot of positive effects, such as having fun and being popular

Strongly disagree Disagree Agree Strongly agree

Q2. Using substances can have a lot of negative effects, such as being bad for your health and getting into trouble

Agree

Strongly agree

Situational Confidence - SCQ8

PART 2: SITUATI		•			
Imagine yourself, as yo situations. Place an X you feel right now that use. In the example be a little less than halfwa	along the line in you would be ab low, the person f	the scale provid ple to resist prob feels that he or s	led to show olem drinkin she is about	how g or	confident other drug
I feel					
0% 25%	X 50%	75%	100%	=	48%
Not at all confident		Totally	100% Confident		
Right now, I feel I wou situations involving		st the urge to di	rink or use o	ther	drugs in
1. Unpleasant emotions	s				
0% 25%	50%	75%	100%	=	%
Not at all confident			Confident		
2. Physical discomfort		,,,,,,,,,,,,,,,,,,,,,,,,,,,,,,,,,,,,,,,			
0% 25%	50%	75%	100%	=	%
Not at all confident		Totally	Confident		
3. Pleasant emotions		,			
0% 25%	50%	75%	100%	=	%
Not at all confident		Totally	Confident		
4. Testing personal cont	rol				
0% 25%	50%	75%	100%	=	%
Not at all confident		Totally	Confident		
5. Urges and temptatio	ns				
0% 25%	50%	75%	100%	=	%
Not at all confident		Totally	Confident		
6. Conflict with others					
0% 25%	50%	7 5 %	100%	=	%
Not at all confident		Totally	Confident		
7. Social pressures					
0% 25%	50%	75%	100%	=	%
Not at all confident		Totally	Confident		
Not at all confident	others				
8. Pleasant times with	OFFIEL2				
	50%	75%	100%	=	%_

Wellbeing – SWEMWBS

Below are some statements about feelings and thoughts.

Please select the answer that best describes your experience of each over the last 2 weeks.

	More	and line	, Source	Ore direction	A CONTRACTOR OF THE PARTY OF TH
I've been feeling optimistic about the future	1	2	3	4	5
I've been feeling useful	1	2	3	4	5
I've been feeling relaxed	1	2	3	4	5
I've been dealing with problems well	1	2	3	4	5
I've been thinking clearly	1	2	3	4	5
I've been feeling close to other people	1	2	3	4	5
I've been able to make up my own mind about things	1	2	3	4	5

Alcohol & Substance Use Problems ESPAD

C21 How likely is it that each of the following things would happen to you personally, if you drink alcohol?

Mark one box for each line.						
	Very	,				Very
	likel	y L	ikel	y Unsure	Unlikel	y un like ly
a) Feel relaxed			\sqsubseteq			
b) Get into trouble with police			\sqcup			
c) Harm my health						
d) Feel happy						
e) Forget my problems						
f) Not be able to stop drinking			\square			
g) Get a hangover						
h) Feel more friendly and outgoing			╚			
i) Do something I would regret	.Ц		\sqsubseteq			
j) Have a lot of fun	-∐		\sqsubseteq			
k) Feel sick	لِا.		Ų	L		
	1		2	3	4	5

C22 BECAUSE OF YOUR OWN ALCOHOL USE, how often during the LAST 12 MONTHS have you experienced the following?

If you haven't used alcohol the last 12 months, please mark zero occasions on all questions. Mark one box for each line.

Number of occasions							
							40 or
	0	1-2	3-5	6-9	10-19	20-39	more
a) Physical fight							🔲
b) Accident or injury	∐	∐	∐	∐	 	∐	∐
c) Serious problems with your parents		∐	Ц				∐
d) Serious problems with your friends	∐	⊢	∐	∐			 
e) Performed poorly at school or work		⊢		⊢		 	
f) Victimized by robbery or theft		⊢	∐		.	 	 
g) Trouble with police	⊢	⊢	⊢		 	⊢	-
h) Hospitalised or admitted to an emergency room	⊢		⊢		 	·	-
i) Engaged in sexual intercourse without a condom	⊢	⊢	⊢	⊢	H	H	-님
j) Engaged in sexual intercourse you regretted the next day							🔲
	1	2	3	4	5	6	7

Motivation – Readiness Ruler

Single item readiness ruler

On the scale below enter how you feel right now about your substance use

1 2 3 4 5 6 7 8 9 10

I never think about my substance use Sometimes I think about using substances less often

I have decided to use substances less often I am already trying to use fewer substances My substance use has changed I use less than before

Family Relationships - Brief Family Relationship Scale

Responses True or False

Cohesion

- 1. In our family we really help and support each other.
- 2. In our family we spend a lot of time doing things together at home.
- 3. In our family we work hard at what we do in our home.
- 4. In our family there is a feeling of togetherness.
- 5. My family members really support each other.
- 6. I am proud to be a part of our family.
- 7. In our family we really get along well with each other.

Expressiveness

- 8. In our family we can talk openly in our home.
- 9. In our family we sometimes tell each other about our personal problems.
- 10. In our family we begin discussions easily.

Conflict

- 11. In our family we argue a lot. (R)
- 12. In our family we are really mad at each other a lot. (R)
- 13. In our family we lose our tempers a lot. (R)
- 14. In our family we often put down each other. (R)
- 15. My family members sometimes are violent. (R)
- 16. In our family we raise our voice when we are mad. (R)

Time Line Follow-Back - TLFB28 - completed using interview rather than self-complete

To help us evaluate your drug use, we need to get an idea of what your use was like in the past _____ days. To do this, we would like you to fill out the attached calendar.

- ✓ Filling out the calendar is not hard!
- √ Try to be as accurate as possible.
- ✓ We recognize you won't have perfect recall. That's OKAY.

✓ WHAT TO FILL IN

- The idea is that for each day on the calendar we want you to indicate whether you "used" or "did not use" drugs.
- On days when you did not use drugs, you should write a "0" in the box.
- On days when you did use drugs, you should put a "√" in the box.

It's important that something is written for every day, even if it is a "0".

√ YOUR BEST ESTIMATE

- . We realize it isn't easy to recall things with 100% accuracy.
- If you are not sure whether you used a certain drug on a Thursday or a Friday of a certain week, give it
 your best guess! The goal is to get a picture of how many days you were using drugs and your patterns
 of use.

√ HELPFUL HINTS

- Holidays such as Thanksgiving and Christmas are marked on the calendar to help you better recall your
 use. Also, think about whether you used drugs on personal holidays and events such as birthdays,
 vacations, or parties.
- If you have regular drug use patterns you can use these to help you recall your use. For example, you
 may have weekend/weekday changes in your drug use or your drug use may be different depending
 where you are or whom you are with.

✓ COMPLETING THE CALENDAR

- A blank calendar is attached. Each day should contain a "0" for no drug use or a "√" for drug use.
 The time period we are talking about on the calendar is
- from ________to ______
- . In estimating your drug use, be as accurate as possible.
- DOUBLE CHECK THAT ALL DAYS ARE FILLED IN BEFORE RETURNING THE CALENDAR.
- Before you start look at the SAMPLE CALENDAR on the next page.

✓ SAMPLE CALENDAR

2000	SUN	MON	TUES	WED	THURS	FRI	SAT
							2
						0	0
S	3	4 Labor Day	5	6	7	8	9
	0	0	✓	✓	✓	0	✓
Е	10	11	12	13	14	15	16
	✓	✓	0	✓	√	0	✓
Р	17	18	19	20	21	22	23
	✓	0	0	0	0	✓	✓
_	24	25	26	27	28	29	30
Т	0	0	✓	0	0	0	✓

Substance Use Screening Questionnaire – SUSQ

"On how many days in the past 28 days have you used alcohol or other illegal substance (list prompt)?"

youthendowmentfund.org.uk

[contact]

@YouthEndowFund

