Multidimensional Family Therapy to reduce alcohol and drug use in adolescents, an individually randomised controlled trial with embedded internal pilot.

University of Kent; Teesside University

Principal investigator: [name]

Multidimensional Family Therapy to reduce alcohol and drug use in adolescents, an individually randomised controlled trial with embedded internal pilot.

Evaluation protocol

Evaluating institution: University of Kent/ Teesside

University

Principal investigator: [name]

Project title ¹	Multidimensional Family Therapy to reduce alcohol and drug use in adolescents, an individually randomised controlled trial with embedded internal pilot.			
Developer (Institution)	MDFT International / Ending Youth Violence Lab / Barnardo's			
Evaluator (Institution)	University of Kent / Teesside University			
Principal investigator(s)	[name]			
Protocol author(s)	[name], [name], [name], [name]			
Trial design	Two-armed individually randomised controlled trial with embedded internal pilot and implementation and process evaluation			
Trial type	Internal pilot / efficacy			
Evaluation setting	Community			
Target group	13-17 years old, who use alcohol and / or drugs and who have offended or are at risk of offending, resident in Newport and Bristol LA			
Number of participants	400, 200 in the MDFT group and 200 in the BAU group.			
Primary outcome and data source	Percent days abstinent from alcohol and/or substance use at month 6, derived from the time line follow back 28 days.			
Secondary outcome and data source	Percent days abstinent from alcohol and/or substance use at month 12, derived from the time line follow back 28 days. Self-reported violent offending behaviour (Self-Report Delinquency Scale) at months 6 and 12),			

Self-report Strengths and Difficulties Questionnaire (SDQ total score, prosocial score, emotional regulation, peer relationships, hyperactivity, conduct, externalising and internalising scores) at months 6 and 12.

Self-report Short Warwick Edinburgh Mental Wellbeing Scale (SWEMWBS) at months 6 and 12.

Alcohol and substance use problems at months 6 & 12, using the problem scale from the European School survey on Alcohol and Drugs (ESPAD).

Self-report Client Service Receipt Inventory (CSRI) to assess police involvement at months 6 and 12 (arrests, cautions, charges, court attendance), educational outcomes (suspensions, exclusions, managed moves) and employment status.

Protocol version history

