What is the effectiveness of MDFT on the frequency of self-reported substance use, measured at 6-months post-randomisation, for young people aged 13-17 years, who are current substance users and involved in criminal activity or considered at risk of becoming involved in criminal activity compared with business as usual.

Secondary research questions

What is the effectiveness of MDFT on the frequency of self-reported substance use, measured at 12-months post-randomisation, for young people aged 13-17 years, who are current substance users and involved in criminal activity or considered at risk of becoming involved in criminal activity compared with business as usual.

ERQ3 What is the effectiveness of MDFT on the frequency of violent offending at 6- and 12-months post randomisation compared with business as usual

- **ERQ4** What is the effectiveness of MDFT on behavioural and emotional difficulties at 6-and 12-months post randomisation compared to business as usual
- **ERQ5** What is the effectiveness of MDFT on mental health and wellbeing at 6- and 12-months post randomisation compared to business as usual
- ERQ6 What is the effectiveness of MDFT on substance use related problems at 6- and 12-months post randomisation compared to business as usual
- ERQ7 What is the effectiveness of MDFT on substance use related problems at 6- and 12-months post randomisation compared to business as usual
- **ERQ8** What is the effectiveness of MDFT on the frequency of criminal justice outcomes, arrests, cautions, charges and court attendance, at 6- and 12-months post randomisation compared to business as usual
- **ERQ9** What is the effectiveness of MDFT on the frequency of educational outcomes, suspensions, exclusions and managed moves, at 6- and 12-months post randomisation compared to business as usual
- ERQ10 What is the cost per participant associated with the delivery of MDFT
- **ERQ11** To develop a prognostic model exploring the baseline demographics, psychological and family factors that may impact observed outcomes and using the results to elaborate mechanisms of change and where appropriate revise the intervention logic model.
- **ERQ12** To conduct a latent class analysis to explore potential interactions between population subgroups, intervention received, and outcomes observed. Specific sub-groups include ethnicity, sex, age, offending behaviour and substance use severity.

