Wellbeing will be assessed using the Short Warwick-Edinburgh Mental Well-being scale (SWEMWBS; (Clarke et al., 2011)). SWEMWBS is a 7-item, self-completed scale addressing different aspects of eudemonic and hedonic mental health wellbeing. The scale is validated for adolescents and demonstrates good internal consistency (Ng Fat et al., 2017), and discriminant, construct and convergent validity (McKay and Andretta, 2017, Ng Fat et al., 2017).

We will use questions derived from a Client Service Receipt Inventory (CSRI; (Coulton S et al., 2023) to assess school, work and criminal justice involvement over the previous 6-months. All these outcomes will be assessed at baseline and again at month 6.

To explore the mechanism of change we aim to assess changes in domains that are key targets of MDFT. The Brief Family relationship Scale (BFRS; (Fok et al., 2014)) will be used to assess family conflict and cohesion. Motivation to change will be assessed using the readiness to change ruler (RR; (Maisto et al., 2011)). Self-efficacy will be assessed using the short Situational Confidence Questionnaire (SCQ-8;(Breslin et al., 1998)). Positive and negative Expectancy will be assessed using a four-item expectancy measure (SUE; (Montes et al., 2019)).

Secondary outcomes will be assessed at baseline and at the 6-and 12-month follow-up points and have established psychometric properties in adolescent population. Therapeutic alliance will be assessed using the revised Therapeutic Alliance Scale for Children (TASC-r; (Shirk and Saiz, 1992)) at the 6-month follow-up only.

All outcome measures have been used previously in adolescent populations, and we estimate the outcome data set takes on between 10 and 20 minutes to complete.

Table 4: Core outcomes and the time of data collection.

Outcome	No of items	Baseline	Six months
Stratification			
Global Assessment of Individual Need – short screen (GAIN-SS)	5	✓	
Covariate			
Single Substance Use Question – 28 day (SUSQ28)	1	✓	
Primary			
Time Line Follow-Back – 28 (interview)			✓
Secondary			
Self-reported delinquency (SRDS) ¹	36	✓	✓
Strength and Difficulties (SDQ) ¹	25	✓	✓
Wellbeing (SWEBWMS)	7	✓	✓
Family cohesion and conflict (BFRS)	15	✓	✓
Alcohol and substance use problems (ESPAD)	8	✓	✓
Client Service Utilisation (CSRI)	8	✓	✓
Exploratory			
Motivation to change (RR)	1	✓	✓
Substance use expectancy (SUE)	4	✓	✓
Substance use efficacy (SCQ8)	8	✓	✓
Therapeutic Alliance (TASC-r)	12		✓

¹SRDS and SDQ are YEF core outcomes.

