Changes in the frequency, quantity and type of substances is assessed using the time line follow-back method over a 28-day retrospective period (TLFB 28; (Sobell and Sobell, 1995). Violent, non-violent and antisocial behaviour is assessed using the self-report delinquency scale (SRDS; (McAra and McVie, 2007). Emotional regulation, internalising, externalising and prosocial behaviours, and conduct issues are assessed using the strengths and difficulties questionnaire (SDQ; (Goodman, 1997)). Wellbeing and mental health are assessed using the Warwick Edinburgh mental wellbeing scale (WEMWBS; (Clarke et al., 2011)). The frequency of school attendance, exclusion, suspensions and involvement with the police and criminal justice system is assessed using a short form client service receipt inventory validated in other studies of adolescent substance using populations (CSRI; (Coulton S et al., 2023, Coulton et al., 2024)). Substance use related problems are assessed using the European School Project on Alcohol and Drugs problem domain (ESPAD; (Group, 2021).

Long term outcomes

Long term outcomes occur beyond the horizon of the trial. They are considered as longer-term impacts associated with changes observed in the short-term outcomes. Sustained reductions in substance use. Greatly reduced violent and non-violent offending due to reductions in risk factors associated with offending behaviour and fewer externalising and conduct behaviours. Improved educational attainment due to reduced absenteeism and less disengagement with education leading to increased propensity to remain in education or transition to employment. Improved physical and psychological health due to reduced substance use and fewer internalising behaviours and a more positive transition to adulthood.

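### The ESPAD problem items shown ask only about alcohol and over 12 months, so the form does not match the outcome alcohol and substance use problems at month 6 (window and drugs) or month 12 (drugs)

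*Protocol*

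**What the plan says.** The summary table at the front of the protocol lists as a secondary outcome: "Alcohol and substance use problems at months 6 & 12, using the problem scale from the European School survey". Table 1 repeats the construct. ERQ6 and ERQ7, which are worded identically, ask: "What is the effectiveness of MDFT on substance use related problems at 6- and 12-months post randomisation". Appendix I (Short term outcomes) ties construct to instrument: "Substance use related problems are assessed using the European School Project on Alcohol and Drugs problem domain".

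Appendix IV reproduces the form under a heading that names both alcohol and substance use. It has two blocks:

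- **C21** (11 items) asks how likely various effects would be if the respondent drank alcohol. These are expectancies, with no recall period.
- **C22** (10 items) is the only problem block. Its stem is "BECAUSE OF YOUR OWN ALCOHOL USE, how often during the LAST 12 MONTHS have you experienced the following", followed by the instruction "If you haven't used alcohol the last 12 months, please mark zero occasions on all questions".

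Table 4 gives the ESPAD measure 8 items. No drug-inclusive stem, shorter window or planned rewording appears anywhere in the protocol.

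**The concern.** The outcome's name and the research questions cover alcohol and drugs. The items shown attribute problems to alcohol alone. Inclusion criterion 3 admits young people on alcohol or substance use, so someone who uses drugs and does not drink can be randomised, and the form tells that person to enter zero throughout. Those who use both are asked only about the harm they put down to alcohol. An effect of MDFT on drug-related problems could not be seen at either follow-up.

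The recall period raises a separate issue at month 6. A 12-month look-back from that visit takes in six months before allocation, when no treatment effect is possible. The other event measures avoid this: the SRDS and the CSRI both look back six months, which matches the follow-up interval.

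Neither defect can be repaired in a statistical analysis plan. Answers to questions never asked cannot be recovered, and a 12-month category cannot be split into parts before and after randomisation.

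**Working it through.** **1. Construct against form**

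| Source in the protocol | Substances | Window |
|---|---|---|
| Summary table, Table 1, ERQ6/ERQ7, Appendix I | alcohol and other substances | months 6 and 12 |
| Appendix IV, C22 (problems) | own alcohol use only | last 12 months |
| Appendix IV, C21 (expectancies) | alcohol only | none |
| SRDS (Table 1), CSRI (Secondary outcomes) | not applicable | previous 6 months |

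Elsewhere in Appendix IV the GAIN-SS, SCQ8 and SUSQ are worded for alcohol and other drugs, so drug-inclusive wording is already in use in this trial.

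**2. Share of the recall window before randomisation**

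Share = max(0, window − months since randomisation) / window.

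- Month 6, 12-month window: (12 − 6)/12 = 50%.
- Month 12, 12-month window: 0%.
- Month 6, 6-month window: 0%.

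**3. Effect on an event count (illustration)**

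Assume a constant event rate λ per month, equal in both arms before randomisation, and a relative reduction e afterwards. The month-6 count in the MDFT arm is 6λ + 6λ(1 − e) = 12λ(1 − e/2). A 20% reduction would therefore appear as 10%. C22 records ordinal bands (0, 1-2, 3-5 and so on up to 40 or more), so this halving does not carry over exactly to the recorded score.

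**4. Effect on power (illustration)**

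The protocol gives no effect size, correlation or event rate for the ESPAD score. To show scale only, take the planning values for the primary outcome: d = 0.27, r = 0.4 and 182 per arm. With baseline adjustment, power ≈ Φ(d/√(1 − r²) × √(182/2) − 1.96). For those values d/√(1 − r²) = 0.2946, times √91 = 9.539 gives 2.810, and Φ(0.850) = 80%, which is the protocol's planning power.

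Now divide time into three 6-month periods: P1 and P2 before randomisation, P3 after it. Assume equal variances and a common pairwise correlation ρ. The 12-month baseline score is P1 + P2 and the month-6 score is P2 + P3. Then:

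- correlation of the two scores: c = (1 + 3ρ)/(2 + 2ρ)
- standardised effect on the month-6 score: 0.27/√(2 + 2ρ)
- effect after baseline adjustment: that value divided by √(1 − c²)

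With 6-month windows the scores are P2 and P3, the correlation is ρ, and the adjusted effect is 0.27/√(1 − ρ²).

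| ρ (assumed) | c | Power, 12-month window | Power, 6-month window | Loss (points) |
|---|---|---|---|---|
| 0.2 | 0.67 | 60.7% | 74.8% | 14 |
| 0.4 | 0.79 | 70.1% | 80.2% | 10 |
| 0.6 | 0.875 | 84.5% | 89.6% | 5 |

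For ρ = 0.4: c = 2.2/2.8 = 0.786; 0.27/√2.8 = 0.1614; divided by √(1 − 0.786²) = 0.6186 this gives 0.261; times 9.539 gives 2.488; Φ(0.528) = 70%.

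**5. Item count**

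Table 4 says 8. C22 has 10, C21 has 11, together 21. None of these matches.

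**The case against.** **The appendix page may not be the form that is fielded.** Appendix IV looks like a set of source forms. The TLFB sheet has a blank recall period and a calendar for 2000 with US holidays. It asks only about drugs although the outcome includes alcohol. The BFRS shows 16 items against 15 in Table 4. The 8 ESPAD items in Table 4 match neither block, and tools are to be agreed with the youth panel before use. This stands as a limit: one cannot say with certainty what will be asked. It does not remove the point, because no 8-item, drug-inclusive or 6-month version is shown. If one is intended, the appendix is wrong and still needs correcting.

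**Drug-related problems are asked about somewhere.** GAIN-SS items c to e cover problems from alcohol or other drugs. Table 4 schedules the GAIN-SS at baseline only, so it cannot serve as the follow-up outcome.

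**A stronger reading is tempting.** A reader might halve d from 0.27 to 0.135, keep r = 0.4 and conclude that month-6 power falls from 80% to 29% (0.135/√0.84 × √91 = 1.405; Φ(−0.555) = 29%), so that a null result would mean nothing. The documents do not support this. Both inputs belong to the primary outcome. Holding r at 0.4 also ignores that the 12-month baseline and month-6 windows share six months, which raises their correlation, and the Efficacy study analysis section puts baseline covariates in the secondary-outcome models.

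**Two further overreadings.** The zero score applies only to someone with no alcohol use in 12 months, and the protocol gives no prevalence for that group. And nothing states that C21 is scored as part of the problem scale.

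**Conclusion.** The mismatch holds on the protocol's own text, on the condition that C22 is the form used. The gap on drug-related problems then affects both follow-ups and limits ERQ6/ERQ7 to alcohol. The window problem affects month 6 only, where exactly half of the recall precedes randomisation.

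The 50% share needs no modelling. The cost in power does, and the protocol lacks the inputs. The range of about 5 to 14 points rests on borrowed planning values, a score treated as linear, equal variances, period correlations of 0.2 to 0.6, adjustment for the baseline score, and consistent recall of the shared months. Inconsistent recall would make the loss larger. A month-6 null would be harder to read, but not uninterpretable.

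This is a should-fix. It concerns one secondary outcome and leaves the TLFB primary outcome, the sample size and the other secondary outcomes as they are.

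**What to change.** State in the outcome section and Appendix IV exactly which ESPAD items form the problem score. Word the stem for problems due to the participant's own alcohol or other drug use, over the last six months, at baseline, month 6 and month 12, in line with the SRDS and CSRI. Adapt the instruction to non-drinkers accordingly. State that C21 is not part of the problem score, and correct the item count in Table 4.

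The form change itself is cheap if made before the first baseline assessment. The real cost is departure from the published wording: comparability with published ESPAD figures is lost, and the psychometric support that the protocol relies on for its secondary outcomes would no longer apply directly to this scale.

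If the C22 stem is kept as printed in Appendix IV, rename the outcome alcohol problems, treat month 12 as its post-randomisation assessment, and limit ERQ6/ERQ7 to alcohol. That costs nothing in data collection but gives up the question about drug-related problems.
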